## Suubi4Her Proposal

Final Version: 7-September-2017

**Study Overview.** The Suubi4Her program will test the effects of a combination asset-based financial inclusion intervention (YDAs) with an evidence-based family strengthening intervention to be delivered via multiple family groups (MFG) to understand the effects and costs associated with a combined intervention versus YDA alone. Specifically, the proposed study addresses three study aims:

**Aim 1.** Examine whether the *Suubi4Her* intervention is effective in protecting adolescent girls against known HIV risk factors (including economically-motivated sex and intimate partner violence).

**Aim 2.** Elucidate the effects of the *Suubi4Her* intervention on behavioral health functioning (i.e., depression, self-efficacy and hopelessness) and examine the effects of these variables as potential mechanisms of change, mediating the relationship between each intervention and HIV risk reduction.

**Aim 3.** Evaluate the cost-effectiveness of each intervention condition.

To address the three aims guiding the proposed study, we will randomize girls (at the school level) to one of three study conditions: 1) YDA condition with a 1:1 saving incentive match rate – for educational purposes and microenterprise development (n=420 participants; n=14 schools); 2) YDA + MFG intervention condition (n=420 participants; n=14 schools); 3) A control condition receiving standard health and sex education provided in schools (n=420 participants; n=14 schools). We detail the three study arms below.

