**Assessments.** We will have four assessment points: baseline (pre-test), 12, 24, and 36-months post-intervention initiation. All Assessments will take place at the child's home with each lasting about 60 minutes. Although all the children will be attending school, and we expect all of them to be English-speaking (the instructional language in all Ugandan schools), assessments will be conducted in English or Luganda (local language) depending on participants' English proficiency. All interviewers will be fluent in English and Luganda. Questions will be translated from English to Luganda and back-translated by a certified translator from a local University (Department of Languages) following standard procedures. Drs. [name] and [name] (fluent in Luganda and English) will cross-check all translated assessments. All interviewers will receive a highly structured and intensive training conducted by Drs. [name] and [name]. All measures used have been or will be pre-tested and made culturally appropriate to the Ugandan context. For questions measuring sensitive behaviors (i.e., sexual risks), we will use Audio Computer-Assisted Self-Interviews (ACASI) where the participant takes the survey herself on a mini laptop. Non-sensitive questions will be interviewer-administered.

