**Study Population.** A total of 1260 secondary school-going girls (ages 15-17 at enrollment) in their first year of secondary school will be enrolled and followed for the 12 academic terms (through the last year of lower secondary school—Senior 4). To avoid stigma that surrounds being HIV positive in the region, no girl will be excluded by virtue of their HIV status. Rather, girls who test HIV positive during the baseline interviews will be referred for care and support (in the event they are not already in care) to our extensive network of collaborating clinics and NGOs in the study area, depending on the girl's preference. Once a girl has been linked to care, we will follow-up within thirty days to ensure she has been enrolled. We will also verify whether the referred girls are engaged in care during our follow-up interviews. Similarly, girls testing positive for pregnancy will be linked to antenatal care services at an existing health facility of their choice, and will thereafter be followed up by peer mothers for peer support while those testing positive on STIs (Gonorrhea, Trichomonas and Chlamydia) will be linked to STI treatment clinics offering adolescent-friendly services, or to the Rakai Health Sciences Program STD clinic, whichever the participant prefers. Girls will not be excluded for pregnancy status nor STI/STD status.

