#### **Selection of Participants**

The target population for this study are older adolescent girls (ages 15-17 at enrollment), in secondary school and living within the four districts of Uganda: Masaka, Rakai, Lwengo and Kalungu. HIV prevalence in this region is 9.8%, compared to other regions in Uganda (7.3%).

**Inclusion Criteria:** Specifically, for an adolescent to be included in the study, she will have to meet the following criteria: (1) female; (2) enrolled in her first year of secondary school (senior

1) in Rakai, Masaka, Lwengo or Kalungu districts; (3) age 15-17 years; (4) living within a family (broadly defined and not an institution or orphanage, as those in institutions have different familial needs).

**Exclusion criteria:** Girls are ineligible if: (1) they have a cognitive or severe psychiatric impairment that would prevent comprehension of study procedures as assessed during the Informed Consent process (see Recruitment and Consent Section) or; (2) they are unwilling or unable to commit to completing the study.

We will not exclude girls because of their HIV, STI and/or pregnancy status and the analysis will be adjusted to account for these baseline factors. Girls testing positive for HIV, STI (Gonorrhea, Trichomonas, or Chlamydia) or pregnancy will be referred for care and support (see *Study Population* above). A plethora of services, including access to free antiretroviral therapy (ART), and counseling exist for children and adults living with HIV in the study region. We will follow up with all girls who test positive for HIV or an STI within 30 days of referral, to check on their engagement in care. For girls who test HIV positive, engagement in care will be verified annually using clinical and viral load records.

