Our primary interest is to estimate the marginal or population-average effects of intervention participation on HIV risk outcomes rather than the effect for a hypothetical average subject or school. Moreover, within-subject and within-school HIV risk outcome correlations are considered nuisance parameters rather than quantities of interest to be modeled explicitly. Accordingly, generalized estimating equations (GEE) will be used to perform the proposed primary analyses to test Hypotheses H1A-H1C. These hypotheses will be tested by three pairwise planned time-averaged comparisons of post-baseline measurements. Alpha ( $\alpha$ ) will be set at  $.05/3=.017$  for these three planned comparisons to maintain a nominal  $\alpha=.05$ . Any additional post-hoc comparisons (e.g., paired comparisons of groups at each time point) will maintain nominal alpha of .05 through the use of simulation-based stepdown multiple comparison methods. The alternating logistic regression (ALR) approach implemented in SAS PROC GENMOD will be used to address the 3-level clustering of observations within participants and participants within schools. Though GEE estimates are consistent even if the correlation structure is misspecified, GEE's statistical efficiency improves as the working correlation structure more closely approximates the actual correlation structure; therefore, various correlation structures suitable for the study's design will be considered (e.g., exchangeable; nested-1). The QIC statistic will be used to select the final correlation structure. Randomization strata indicators will be included as covariates as required by the stratified randomized design to obtain unbiased inferences. Additional covariates (e.g., HIV serostatus) will be included if they improve QIC. Robust Huber-White "sandwich" standard errors will be used to obtain correct inferences even if the chosen correlation structure remains slightly misspecified. GEE case deletion diagnostics (e.g.,

DFBetas, Cook's *D*) will be used to investigate whether influential cases are present; if such cases are found, results will be reported with and without influential cases included.

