**Primary analyses for Specific Aim 2.** For Specific Aim 2, *Elucidate the effects of the Suubi4Her interventions on behavioral health functioning (i.e., depression, self-efficacy and hopelessness) and examine the effects of these variables as potential mechanisms of change, mediating the relationship between each intervention and HIV risk reduction*, we hypothesize that following baseline participants in:

1. H2A: YDA will have higher mean mental health functioning vs. control participants;
2. H2B: YDA+MFG will have higher mean mental health functioning vs. control participants, and
3. H2C: YDA+MFG will have higher mean mental health functioning vs. YDA participants.

[figure not shown]
The same GEE-based approach as described above in the primary analysis for Specific Aim 1 will be used to test H2A-H2C, except that instead of the odds of a binary outcome being estimated, the GEEs for H2A-H2C will employ appropriate distributions and link functions suitable for modeling the means of continuous mental health outcomes (e.g., normal distribution and identity link function). Robust Huber-White "sandwich" standard errors will be used to obtain correct inferences even if the chosen correlation structure remains slightly misspecified or if residual distributions are not perfectly normal or homoscedastic.

**Aim 3: Evaluate the cost-effectiveness of each intervention condition.** Following standard practice of measuring cost-effectiveness of interventions, we will measure costs on a per person basis. The intervention costs will include all program costs, including not just the YDA savings match, but also all costs incurred for running the program. Research costs will not be included. Data on the savings match costs will be readily available from the management information system. Data on costs of other program elements will be drawn from project administrative records and collected throughout the intervention period. In the analyses, costs from multiple years will be adjusted for inflation, depreciation, and discounting.

We will estimate how much *Combined Intervention (YDA + MFG)* vs *YDA-alone* increased particular outcomes, such as schooling. The per-person costs of *YDA + MFG*, and *YDA alone* will then be divided by the relevant effect sizes to produce estimates of cost-effectiveness.

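### The Aim 2 model does not prespecify the girl's baseline score on the scale analysed; it should be a fixed covariate, not left to QIC

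*Combined protocol and SAP*

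**What the plan says.** All references are to the combined protocol and SAP.

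- **Test.** In Data Analysis Plan and Statistical Procedures, the Aim 1 paragraph defines the tests as "three pairwise planned time-averaged comparisons of post-baseline measurements", fitted by GEE.
- **Aim 2 model.** The Aim 2 paragraph states: "The same GEE-based approach as described above in the primary analysis for Specific Aim 1 will be used to test H2A-H2C". Only the distribution and link change, to suit continuous outcomes. A typical hypothesis is H2A: "YDA will have higher mean mental health functioning vs. control participants".
- **Covariates.** The Aim 1 paragraph puts indicators for the randomization strata in the model. Further covariates enter if they improve QIC; HIV serostatus is the one example, and the candidate list is open.
- **Other baseline adjustment.** Selection of Participants says of HIV, STI and pregnancy status that "the analysis will be adjusted to account for these baseline factors". None of these is an Aim 2 outcome.
- **Visits.** The Assessments paragraph says: "We will have four assessment points: baseline (pre-test), 12, 24, and 36-months post-intervention initiation".
- **Size.** Each arm is described as "n=420 participants; n=14 schools".

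No sentence places the baseline depression, hopelessness or self-efficacy score in the Aim 2 model, and none excludes it. No baseline-constrained longitudinal model is described either.

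**The concern.** For a repeatedly measured continuous scale, the girl's own earlier score is usually the strongest available predictor of her later scores. With 14 schools per arm, two arms can differ at baseline by chance by about as much as the standard error of the effect. If the score is not in the model, that difference carries through into the post-baseline contrast in whichever direction it happens to fall.

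At stake are the precision and power of three primary Aim 2 comparisons, each tested at .05/3. A second problem is that whether the score enters at all is settled by a fit criterion computed on outcome data, possibly differently for each scale.

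**Working it through.** **Inputs from the documents.** 420 girls and k = 14 schools per arm, so m = 420/14 = 30 girls per school; 3 post-baseline visits; alpha .05/3 = .0167 per comparison. The plan gives no power figure to reproduce.

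**Assumptions.** Outcome SD 1; no dropout; two-sided tests (sidedness is not stated); ICC .01 to .10; girl-level correlation between visits r = .3 to .6; school-level correlation s from r up to .8. Strata are ignored.

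**Formulas for school means.**

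- Mean of three follow-ups: V_Y = ICC(1+2s)/3 + (1−ICC)(1+2r)/90
- Baseline: V_X = ICC + (1−ICC)/30
- Covariance: C = ICC·s + (1−ICC)r/30
- Adjusted for the girl's score and its school mean: V_Y − C²/V_X
- Adjusted for the girl's score alone, pooled slope b = ICC·s + (1−ICC)r: V_Y − 2bC + b²V_X
- SE of the difference between two arms = √(2V/14)

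**Chance baseline difference.** Its SD is √(2V_X/14). At ICC .05, V_X = .05 + .95/30 = .0817, so the SD is .108. At ICC .01 and .10 it is .078 and .136.

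**Worked case, ICC .05, r = s = .5.** V_Y = .0333 + .0211 = .0544, so the unadjusted SE is √(2 × .0544/14) = .088. When s = r, adjustment multiplies the variance by 1 − 3r²/(1+2r) = 1 − .75/2 = .625, giving SE .070, a cut of 21%. That is worth 14/.625, or about 22 unadjusted schools per arm. The effect detectable with 80% power (noncentral t, 26 df) falls from .30 to .24 SD.

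**Range.**

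| ICC | r | s | SE unadjusted | SE, girl's score | SE, plus school mean | Cut |
|---|---|---|---|---|---|---|
| .01 | .3 | .3 | .057 | .052 | .052 | 9% |
| .05 | .5 | .5 | .088 | .070 | .070 | 21% |
| .05 | .5 | .8 | .096 | .064 | .061 | 33%, 36% |
| .10 | .3 | .8 | .121 | .090 | .077 | 26%, 36% |
| .10 | .6 | .8 | .125 | .073 | .070 | 42%, 43% |

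Where two cuts are shown, the first uses the girl's score alone and the second adds the school mean. In the fourth row, if the fitted slope is r rather than the pooled value, the first cut is 23%.

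**Power.** An effect with 80% power unadjusted would have about 87% to 88% at the 9% cut, 95% at the 21% cut and over 99% at the 43% cut.

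**Bias check.** In a 4,000-replicate simulation of the worked case with a true effect of .20, the unadjusted estimate averaged .199 (SE .089) and correlated .61 with the chance baseline difference. The algebra gives .5/√(2/3) = .61. The estimate adjusted for the girl's score averaged .200 (SE .071), with correlation about 0.

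**The case against.** The strongest reply is that the plan does not leave the score out. Its candidate list is open, and a strongly prognostic score would very probably pass. In a simulation of 42 schools of 30 girls at a weak setting (ICC .02, r = .3, s = .5), QIC chose the model with the score in 40 of 40 runs. This stands: a reader might infer that Aim 2 is analysed without the baseline score, and the text does not support that. But the score must first be offered as a candidate, and no passage says it will be.

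A reader might also infer bias or invalid inference. The documents do not support that either: schools are randomized, and the plan models school clustering with robust standard errors. What remains is lost precision and sensitivity to chance imbalance in the one trial that is run.

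Third, the size rests wholly on assumptions, and the strata may already absorb some between-school variance. This stands too.

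Fourth, one might extend the point to Aim 1's self-reported behaviours. The plan targets population-average effects there, and under a logit link adding the girl's baseline behaviour makes the odds ratio conditional on it. Illustration, all values assumed: baseline prevalence 20%, baseline-behaviour odds ratio 10, control risk 10% without the behaviour, conditional odds ratio .60. Control risk is .8 × .100 + .2 × .526 = .185 and intervention risk is .8 × .0625 + .2 × .400 = .130. The marginal odds ratio is (.130/.870)/(.185/.815) = .66. The calculations above concern continuous outcomes and do not support an Aim 1 change.

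**Conclusion.** The point holds as a gap in prespecification. The Aim 2 model does not commit to the baseline score of the outcome being analysed, and its inclusion is left to a data-driven rule. The unadjusted contrast would be unbiased on average but less precise than it need be.

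On the assumed inputs the SE reduction is roughly 9% to 43%. The lower end applies when both correlations are .3; the upper end needs school-level correlation near .8. Most of the gain comes from the girl's own score. The school mean adds a clear amount only where school-level correlation is well above girl-level correlation, as in the fourth row of the table.

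That each Aim 2 scale is measured at baseline is inferred from the assessment schedule, since the text has no instrument-by-visit table. The change is worth making before analysis; its absence does not invalidate the trial.

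**What to change.** Add to the Aim 2 paragraph:

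> Every H2A-H2C model includes the girl's baseline score on the same scale as a fixed covariate, not subject to QIC selection. Girls with a missing baseline score are kept, using mean imputation and a missingness indicator.

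Optionally, prespecify the school mean of the baseline score as a second fixed term. Confirm in the text that each scale is administered at baseline.

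Leave the Aim 1 logistic models as they are on this point, or add baseline behaviour only together with standardization back to the marginal odds ratio.

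The cost is one or two model terms per outcome plus the missingness indicator. No extra visits are needed if the scales are in the baseline interview.

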SSA remains the world's most affected region in the HIV epidemic (UNAIDS, 2014) with girls accounting for 7 out of 10 new infections among adolescents (ages 15-19 years) (UNICEF, 2016). This gender disparity has increased recognition that adolescent girls need more attention in the fight against HIV/AIDS in the region.

Given the complex and multi-dimensional reasons for increased HIV risk among adolescent girls in SSA, and the failure of most single interventions to significantly decrease these rates, UNAIDS and others in the HIV research community have observed an urgent need for strategies to shift towards Combination HIV Prevention (CHP) (Hankins & de Zalduondo, 2010; UNAIDS, 2010). This is the reason for the proposed *Suubi4Her* study aimed at testing the impact of a combination family-based economic empowerment through Youth Development Accounts (YDAs) with an evidence-based family strengthening intervention delivered via multiple family groups (MFG). The study design will allow us to examine and understand the effects and costs associated with each of these interventions individually, and in combination.

The proposed *Suubi4Her* study uses a combination intervention to address multiple layers of girls' transitions both on the individual and familial levels. Specifically, the *Suubi4Her* study will examine questions regarding impact using both objective and subjective measures, scale-up, and cost of the intervention for an older age group and the extent to which a combination intervention will protect older girls against known HIV risk factors and enhance several

outcomes: financial stability (asset-accumulation), educational achievement (school enrollment, attendance, and attainment), sexual risk-taking behavior, and mental health functioning.

In summary, the proposed study innovates by testing an innovative combination intervention that has a potential to promote sustainable behavioral change among older adolescent girls by use asset-development incentives (savings match) and behavioral economics principals.

**Design and Methods.** The proposed study examines the effectiveness of: 1) the combined YDA+MFG vs. YDA-alone; 2) YDA + MFG vs. Usual Care; and 3) YDA vs. Usual Care, and determine key factors influencing scale up via a three cluster randomized control trial (RCT). The three groups include: 1) YDA condition with a 1:1 saving incentive match rate; 2) Combined YDA+MFG intervention condition; 3) Usual Care alone.

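### Aim 3 fixes neither the outcome nor any uncertainty for its cost-effectiveness ratio, so it can give one cost figure for an effect compatible with zero

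*Combined protocol and SAP*

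**What the plan says.** The method is in the Aim 3 text of Data Analysis Plan and Statistical Procedures.

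- **Cost:** "we will measure costs on a per person basis". All programme costs count and research costs do not. The only adjustments stated are that "costs from multiple years will be adjusted for inflation, depreciation, and discounting".
- **Effect:** the plan will estimate how much the combined arm, compared with YDA alone, "increased particular outcomes, such as schooling".
- **Ratio:** the per-person costs of the two arms "will then be divided by the relevant effect sizes to produce estimates of cost-effectiveness".

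Study Overview and Study Significance mention cost and cost-effectiveness but add no method. Study Significance lists the outcomes the study hopes to improve: asset accumulation, "educational achievement (school enrollment, attendance, and attainment), sexual risk-taking behavior, and mental health functioning".

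For Aim 1 the same section plans robust sandwich errors, "standard errors will be used to obtain correct inferences even if the chosen correlation structure remains slightly misspecified", and an alpha of .05/3 = .017 "for these three planned comparisons to maintain a nominal" level of .05. Aim 2 reuses that approach. The Aim 3 text refers to neither.

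**The concern.** Two things are left open.

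1. **Uncertainty.** Dividing a cost by an estimated effect gives a number whatever the precision of the effect. If the effect's confidence interval includes zero, the matching interval for the ratio has no finite upper limit and also takes in negative values. The plan states no interval, resampling method, sensitivity analysis or rule for a null or negative effect. Schooling, the only example given, is in neither the Aim 1 nor the Aim 2 hypotheses, so no model or standard error is stated for it at all.

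2. **Denominator.** The outcome is not named, and nor are its scale or time point. Several candidates are listed elsewhere, and nothing prevents the choice from being made once the effects are known. Choosing the largest effect makes the programme look cheaper.

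Aim 3 is one of three stated aims, and the protocol plans dissemination to stakeholders. A cost figure without its uncertainty, or for an outcome chosen late, could be read as firmer than it is.

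**Working it through.** The documents state no ratio, threshold, effect size, standard deviation or intraclass correlation (ICC), so there is no Aim 3 figure to reproduce. The following shows how the stated rule behaves. Only the design figures come from the documents.

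**Inputs from the documents.** 420 girls in 14 schools per arm (Study Overview), so 420/14 = 30 girls per school on average.

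**Assumed, not in the documents.** Cost C known without error; ICC .01 to .10; the true effects below; equal school sizes; one measurement; no dropout; normal approximation.

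**Step 1: when the ratio has no finite interval.** With C fixed and a 95% effect interval (L, U), the set for C/effect runs from C/U to C/L if both limits are positive. If L < 0 < U, it is everything above C/U together with everything below C/L, which is unbounded. For a true effect of z standard errors,

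P(unbounded) = Φ(1.96 − z) − Φ(−1.96 − z).

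- z = 1: Φ(0.96) − Φ(−2.96) = .830
- z = 2: Φ(−0.04) − Φ(−3.96) = .484
- z = 3: Φ(−1.04) − Φ(−4.96) = .149

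**Step 2: what z might be in this design.** Design effect = 1 + 29 × ICC; effective n per arm = 420/design effect; SE of a standardised mean difference = √(2/effective n).

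- ICC .01: design effect 1.29, effective n 325.6, SE .078
- ICC .05: design effect 2.45, effective n 171.4, SE .108
- ICC .10: design effect 3.90, effective n 107.7, SE .136

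Share of trials with an unbounded ratio:

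| True difference | ICC .01 | ICC .05 | ICC .10 |
|---|---|---|---|
| 0 | 95% | 95% | 95% |
| 0.1 | 75% | 85% | 89% |
| 0.2 | 28% | 54% | 69% |
| 0.3 | 3% | 21% | 40% |

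If the true effect is zero, half of trials still give a positive estimate, and 47.5% give one that is positive but not significant at the two-sided 5% level. Each of these yields a finite, favourable-looking ratio.

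**Step 3: one worked case.** Suppose 83% and 80% of girls are in school in the two arms, with ICC .05. SE = √[(.80 × .20 + .83 × .17)/171.4] = .0419. The difference is .03, with 95% CI .03 ± 1.96 × .0419 = −.052 to .112. For a cost of 100, the rule prints 100/.03 = 3333 per extra girl in school. The interval starts at about 892, has no upper limit and also has a negative branch. At ICC .01 the finite limit is 1116 and at ICC .10 it is 748; both sets are still unbounded.

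**Step 4: the open denominator.** If no outcome is truly affected, the chance that at least one estimate is favourable is 50% for one outcome and 1 − 0.5³ = 87.5% for three independent outcomes (75% if they are correlated at .5). A favourable-looking denominator would then usually be available.

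**The case against.** **The plan does not rule out intervals.** This is correct. The text speaks of effect sizes, not point estimates, and Aim 1 or Aim 2 effects would come with sandwich errors. A reader might infer that the sponsor intends a bare ratio or means to pick the outcome late. The documents say neither. What stands is that no uncertainty method and no outcome are stated for Aim 3, although Aims 1 and 2 do state their inference.

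**The percentages are not about this trial.** This is also largely correct. Step 1 is one minus power at an assumed effect-to-SE ratio and would hold for any trial. Step 2 uses the trial's own cluster sizes, but its ICC and effects are assumed. The gap follows from the text and does not depend on them.

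**Schooling is a legitimate outcome.** Study Significance includes "educational achievement (school enrollment, attendance, and attainment") among the outcomes to be enhanced, and the Aim 3 wording in Study Overview is not limited to HIV risk. A reader might infer that schooling is the wrong denominator; the documents do not support that. It simply does not price the HIV-risk reduction of Aim 1.

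**Why not report a ratio only when the effect is significant?** That would filter on significance and bias what is reported. With cost fixed and only favourable estimates above 1.96 SE reported, the median estimate is z + Φ⁻¹(1 − ½[1 − Φ(1.96 − z)]) standard errors. This is 2.38, 2.65 and 3.19 for z = 1, 2 and 3, so the median reported cost per unit is understated by 1 − 1/2.38 = 58%, 1 − 2/2.65 = 25% and 1 − 3/3.19 = 6%.

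**Joint resampling of costs has limits.** Match data are to come from the management information system, and monthly statements per girl make a per-girl match cost likely. Other costs come from administrative records, with no breakdown per girl or school stated. The YDA is meant to run identically in both intervention arms, so the element that differs between them is MFG, and its cost may exist only as an average. This objection stands and shapes the fix.

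**Conclusion.** The point holds. As written, Aim 3 yields a single cost-per-effect figure even when the effect is compatible with zero, on an outcome, scale and time point that can be settled after effects are seen. No other part of the document supplies what is missing.

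The size cannot be fixed from the documents. On the assumptions shown, the ratio has no finite 95% interval in 83%, 48% and 15% of trials at true effects of 1, 2 and 3 standard errors. These are illustrations, not forecasts for this trial. The matter bears on a stated aim but not on the Aim 1 efficacy tests, so it should be corrected without calling those tests into question.

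**What to change.** Before effects are seen, amend the Aim 3 text as follows.

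1. **Name the outcomes.** Include at least one specified HIV-risk or STI outcome from Aim 1, and report schooling as a separately labelled outcome. Aim 1 speaks of STIs and risk behaviours in the plural and singles out no one measure, so the sponsor has to choose. State the time point and use an absolute scale such as a risk difference, because cost divided by an odds-based effect has no clear unit.
2. **Report incremental cost and incremental effect for each pair of arms.** Take joint uncertainty from a bootstrap that resamples whole schools within arm and within randomisation strata.
3. **Handle costs as the data allow.** Use per-girl match cost where available. Enter other programme costs, including MFG, as school or arm averages and vary them in a sensitivity analysis.
4. **Present net benefit or an acceptability curve** over a stated range of willingness to pay. Do this for every named outcome whether or not its effect is significant, with no rule that suppresses results when the interval includes zero.

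The cost is revised analysis-plan wording, a modest amount of extra analysis, and a curve or interval in place of one figure. No new data collection is implied where costs enter as averages.
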